# **Primary Statistical Analysis**

The primary trial outcome is defined as the summed number of different extended spectrum antibiotics received each day, measured repeatedly over the first three days of an admission and divided by the number of days of the admission within the empiric period. An empiric day is a day within the first three days of an admission. We define this outcome as an Extended-Spectrum Days Of Therapy (ES-DOT) per empiric day. For clarity the calculation is as follows: we define a DOT for a particular ES antibiotic as a day in which any number of doses of that antibiotic is given. Different ES antibiotics are summed across the empiric days for each patient admission, then divided by the empiric days for that patient-admission to determine each admission's DOT per at-risk day. If an admission is less than 3 days, only the number of days the patient is admitted will contribute to the numerator and denominator. Antibiotics given during an associated emergency department visit on the date of hospital admission are counted toward the ES-DOT of the first hospital day.

The main trial results will be based upon as-randomized, unadjusted analyses of admission-level ES-DOT per empiric day. We define ES-DOT per empiric day at the individual admission level so that we can perform analyses on individuals.

The trial will be assessed among the cohort of adult admissions who have an ICD-10 claims code indicating UTI is present on admission, who received any antibiotic within 3 days of admission, and who were admitted to a non-ICU location. For admissions initially on a non-ICU floor and transferred to the ICU, analysis will include only admission days on the non-ICU floor within 3 days of admission.

The trial periods are defined as follows: (1) Baseline – April 1, 2017 – September 30, 2018 (18 months); (2) Phase-in – October 1, 2018 – March 31, 2019 (6 months); (3) Intervention – April 1, 2019 – June 30, 2020 (15 months).

The unit of analysis will be individual admissions. Individuals can contribute more than one admission. The analytic model will be a generalized linear mixed effects model for differences in differences, with random effects accounting for correlation within cluster, periodvarying random effects to allow for differences between hospitals from baseline to follow-up, and admission-level random effects to account for correlation within person and hospital. Analyses of the baseline data, performed before randomization, found no evidence of overdispersion in a Poisson model, and so we plan to use that model for analysis of outcomes. The model can be expressed as follows:

$$log(y_{ijph}) = \beta_0 + \beta_1 A_{ijph} + \beta_2 T_{ijph} + \beta_3 A_{ijph} T_{ijph} + b_{0h} + b_{1h} T_{ijph} + g_i$$

where  $y_{ijph}$  is the ES-DOT per at-risk day for patient *i* for admission *j* in period *p* at hospital *h*, and  $A_{ijph} = 1$  if hospital *h* is in the intervention arm and 0 if not, and  $T_{ijph} = 1$  if *p* is the intervention period and 0 if baseline period. The random effects  $b_{0h}$  and  $b_{1h}$  allow for different baseline mean admission-level ES-DOT per at-risk day for each hospital and each hospital per period, respectively, while  $g_i$  allows different admissions to have different mean ES-DOT per atrisk day across multiple admissions. Equivalently, they allow for correlation within hospital at different levels at baseline and at follow-up.

The assessment of trial success will be determined by the significance of the arm by period interaction term  $\beta_3$ , which assesses whether the log relative rate of the outcome due to being in the intervention arm in the intervention period is different from 0. The exponentiated parameter estimate for  $\beta_3$  is the estimated relative rate of ES-DOT per at-risk day due to the intervention, relative to the baseline period. For example, if  $\beta_3$  had a negative value and a p-value <0.05, we would conclude that the patient-specific CPOE smart prompts generated a benefit over routine care. Exponentiating the parameter value would provides an estimate of the relative reduction due to the intervention in the expected ES-DOT per at-risk day.

The primary trial analysis will use an as-randomized unadjusted model with two-tailed significance set at alpha = 0.05. Secondary outcomes also will be assessed using an as-randomized unadjusted model with adjustment for multiple comparisons with two-tailed significance set at alpha = 0.025 for the two secondary outcomes. Subsequent analyses of the primary and secondary outcomes will include both as-treated and adjusted models. Adjusted models will account for individual characteristics such as age, gender, comorbidities, and prior history of MDROs as well as hospital characteristics such as hospital antibiotic resistance. We will also account for randomization units and for seasonality. These analyses will be reported as point estimates with confidence intervals without p-value. The reason for including these analyses is to provide additional information related to the trial outcomes for readers to assess the effects of potential confounders. The reason to not include them in a formal multiple comparisons adjustment is because these analyses are non-independent evaluations relative to the as-randomized unadjusted analyses.

Safety outcomes noted in the above table will be assessed in the most conservative manner to identify potential safety issues. This is required because a reduction in ES-DOT might be achieved only by incorrectly withholding ES antibiotics when they were really needed. Each safety outcome will be evaluated for non-inferiority using an as-randomized unadjusted model with a one-tailed significance set at alpha = 0.05. Analyses planned for these assessments are proportional hazards models with random effects (to account for hospital effects). These models are sometimes called frailty or shared frailty models. Because these are safety outcomes, we do not intend to make adjustments for multiple comparisons in testing them, further increasing conservatism.

All analyses will be performed using current versions of SAS (Version 9.4, as of writing, SAS Institute, Cary NC) and/or R (Version 4.0, as of writing).

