The INSPIRE-ASP Trial is a two-arm cluster-randomized trial in HCA hospitals comparing routine empiric antibiotic prescribing for patients admitted with UTI to prescribing informed by pointof-care precision medicine computerized physician order entry (CPOE) smart prompt for adult patients admitted to general medical or surgical floors. The unit of randomization will be the hospital. The trial will begin with a six-month phase-in period from October 1, 2018-March 31, 2019, followed by a 15-month trial intervention period between April 1, 2019-June 30, 2020. For analysis purposes, the cohort will be defined as adult patients with a primary or secondary claims code indicating UTI that is present on admission, did not transfer directly from the ED to ICU, and is treated with an antibiotic within the first 3 days of hospitalization. A baseline period between April 1, 2017-September 30, 2018 will be utilized for comparison with the intervention period at each hospital. Per guidance from the Office for Human Research Protections (OHRP), prisoners will not be included in this trial. Prescribers and antibiotic stewardship teams in intervention facilities will be trained (e.g., coaching calls, usual communication channels (email, flyers)) that prisoners should be excluded from the trial (i.e., the CPOE smart prompt should not be acted upon for these individuals). Data for any prisoners that may be inadvertently included in study datasets will be removed prior to analyses using claims data as well as admission/discharge/transfer codes indicating 'Court/Law Enforcement'.

B.1.2 HCA Healthcare Infrastructure for the INSPIRE-ASP Intervention Arm

HCA Healthcare currently requires physicians to provide an indication when an antibiotic is ordered (see **Appendix B** for example CPOE indication screens). For facilities assigned to the intervention arm of the INSPIRE-ASP Trial, an INSPIRE CPOE smart prompt will be triggered when physicians prescribe an extended-spectrum (ES, **Table 1**) for a UTI indication in the first three days of a hospital stay. This CPOE smart prompt will provide clinicians with a patient-specific estimate of the likelihood that the UTI is due to the associated target pathogens (e.g. MRSA, VRE, Pseudomonas, ESBL, or CRE, **Table 1**). The smart prompt will also provide guidance for appropriate empiric antibiotic options per trial protocol and hospital policy.

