While this study represents a large cluster-randomized trial of hospitals, simple randomization of hospitals will not ensure balance of key variables by chance alone, and without care could even result in very unequal numbers of hospitals in each arm. Achieving balance on key features of the randomization units (in this case, hospitals) is a critical task in cluster-randomized trials, but little literature on it exists. Unlike individually randomized trials, information about the clusters is often known in advance, but the number of clusters to be randomized can be relatively small. The existence of a priori data can mitigate the small numbers and help to obtain adequate balance through stratification or other methods. One attractive approach is to establish tupletsmatched sets (pairs, for a two-arm trial) – in which one member of each tuplet is assigned to each arm. Schemes for constructing tuplets need not be guided by theory. A formal approach would be to calculate the Mahalanobis distance between hospitals across all key variables and choose the set of tuplets with the minimum average distance. In this approach, we could standardize the variables, and then multiply by values calibrated to reflect any difference in the importance of balancing them. Other approaches are more ad hoc, such as prioritizing broad classes of balance on a key variable and making pairs within these strata based on lower-priority variables. However, there is no "best" method of tuplet construction, only sets that come closer to meeting the varied needs of each trial.

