We will establish the pairs under several plausible tuplet-construction schemes, and use graphical methods to compare all possible realizations for balance between the arms under each scheme. For example, if two variables were to be balanced, we would tentatively divide the sample into two groups under a tuplet construction scheme and then generate a scatterplot showing the between-arm absolute value of the mean difference for one variable on the x-axis and the second on the y-axis for each possible result of the randomization. We would then divide the groups again under the same scheme, and find another point on the scatterplot. Repeating many times would show the typical and distribution of balance under a scheme. Comparing the resulting scatterplots from each tuplet-construction scheme can reveal the relative risks of imbalance and benefits for balance accruing to each randomization scheme, in a practical sense. One tuplet construction method may result in generally close balance on one key characteristic and very variable balance on the other, while a competing scheme has good median balance on both characteristics, but where each has a long tail implying a few bad-luck assignments with poor balance.

We hope to consider balance on more than two factors, and for assessing the impact on balance in this case, we will use a parallel coordinates plot, a multivariate plot method. After determining key variables where balance across the arms would be highly desirable, we will plot the mean difference between the arms for all key variables for each potential realized randomization.

We will focus on balancing the baseline outcome values in participating hospitals and certain key factors that may be associated with UTI such as facility UTI admission volume, local prevalence of antibiotic resistance in UTI patients, length-of-stay, ICU transfers, and facility casemix of patients with UTI. Hospitals that share antibiotic stewardship personnel will be treated as a single hospital unit since the intervention will be overseen by local antibiotic stewardship teams.

B.1.6 Baseline Period Activities

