#### **Power Size/Sample Size Calculations**

Power assessment proceeded as follows, using a Monte Carlo approach. We used available data to define a baseline period of 10/1/2015-12/31/2016 in a bootstrap procedure. Individuals were selected with replacement from within each hospital, once to represent baseline data and separately to represent intervention period data. In the randomization portion of the Monte Carlo approach, we ordered the hospitals by "size", meaning the number of admissions with UTI. Then, within strata of 6 hospitals, we ordered by ES-DOT per at-risk day. Then we took pairs of hospitals with adjacent ES-DOT per at-risk day and assigned one member of the pair to one arm. To do this, a single pseudo-random number uniformly distributed between 0 and 1 was generated for each pair. If it was less than 0.5, the arbitrary "first" member of the pair was assigned to Routine Care and the other to Intervention. If it was greater than or equal to 0.5, then the assignments were reversed. The remaining unpaired hospital of the 59 units were assigned as the "first" member of a pair with no match. (Three sets

of hospitals each shared a stewardship program and these hospitals were treated as a single hospital within the routine.)

If an admission was in the intervention arm in the intervention period, then their ES-DOT per at-risk day was reduced by a proportion, given below. The reduction of ES-DOT per at-risk day was selected with a lower bound determined by the investigators as the hoped-for effect of the intervention with minimal clinical significance, and the impact in the Monte Carlo calculation on a per-admission basis was to reduce the days of therapy proportionately between this number and 1, on a uniform distribution. In other words, if the effect of the intervention was to multiply doses by as little as .9, each person would have their doses multiplied by between .9 and 1. Then an integer value of doses would be chosen as described above.

We are interested in determining whether the patient-specific CPOE intervention reduces ES-DOT per at-risk day by at least 12.5% relative to usual care. Using the method above, we have 97% power (CI 91-99%) to detect this effect. Table 4 below shows the calculated power and confidence intervals for the primary and secondary outcomes to be evaluated in our primary manuscript.

Table 4. Power Calculation – Primary and Secondary Outcomes		
Primary Trial Outcome	Power (CI), %	

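### Should the primary model carry a term for the matched pairs and say which unit its hospital index means?

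*SAP*

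**What the plan says.** Protocol B.1.1 states that "The unit of randomization will be the hospital". Protocol B.1.5 then describes matched sets, pairs in this two-arm trial, "in which one member of each tuplet is assigned to each arm". The pairing scheme is still to be chosen from several candidates. On the matching factors it says "We will focus on balancing the baseline outcome values in participating hospitals", and it adds UTI volume, resistance prevalence, length of stay, ICU transfers and case mix. On shared staff it says "Hospitals that share antibiotic stewardship personnel will be treated as a single hospital unit".

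The SAP's Primary Statistical Analysis section gives a Poisson mixed model with arm, period, arm by period, a hospital effect, a hospital-by-period effect and one further random effect for repeat admissions. In words, the model is set out "with random effects accounting for correlation within cluster, periodvarying random effects to allow for differences between hospitals from baseline to follow-up". The two secondary outcomes are also analysed unadjusted. For the later adjusted models the SAP adds "We will also account for randomization units and for seasonality", and of these supportive analyses it says "These analyses will be reported as point estimates with confidence intervals without p-value".

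The SAP's power section simulates 59 units, ordered by size and grouped in strata of 6: "Then we took pairs of hospitals with adjacent ES-DOT per at-risk day and assigned one member of the pair to one arm". One unit has no match. Three sets of hospitals with a common stewardship programme each count as one hospital there.

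**The concern.** Two things look wrong. First, the design is paired and the analysis is not. If pair mates tend to change alike, the estimate of the arm-by-period effect is more precise than the unpaired standard error shows. The interval would then be wider than necessary, the test would run below 5%, and power might be given away.

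Second, the model speaks only of hospital *h*. If hospitals that were randomised together as one unit were entered as separate clusters, the model would treat linked observations as independent. Type I error on the test that decides trial success would then rise. The SAP mentions randomisation units only for the supportive models, which sharpens the question of what the primary model clusters on.

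**Working it through.** **1. The plan's own figure.** The 97% power comes from a bootstrap of patient data that the documents do not give, so it cannot be reproduced. Its interval can be checked: 97 successes in an assumed 100 replicates give a Clopper-Pearson interval of 91.5% to 99.4%, against the stated 91% to 99%.

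**2. What leaving out pairs can do.** The hospital effect absorbs each unit's baseline level, so only the correlation ρ between pair mates' *changes* matters. The unpaired standard error is proportional to σ, while the true standard deviation of the estimate is proportional to σ√(1−ρ). Hence

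type I error = 2[1 − Φ(1.96/√(1−ρ))].

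| ρ (assumed) | 0 | 0.1 | 0.2 | 0.3 | 0.5 |
|---|---|---|---|---|---|
| 1.96/√(1−ρ) | 1.960 | 2.066 | 2.191 | 2.343 | 2.772 |
| Type I error | 5.0% | 3.9% | 2.8% | 1.9% | 0.6% |

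No non-negative ρ takes it above 5%.

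**3. How much ρ matching on baseline can create.** Scale baseline and follow-up to variance 1 with correlation *r* (not in the documents; assumed). Change has variance 2(1−r) and covariance −(1−r) with baseline. Baseline therefore explains (1−r)²/[2(1−r)] = (1−r)/2 of the variance of change. That is the value ρ would reach under perfect matching on the analysed baseline. The simulation below follows the power routine (59 units, 29 pairs and one single; t-tests on unit-level change; 100,000 replicates).

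| r | Ceiling for ρ, (1−r)/2 | Ceiling for SE ratio, 1/√(1−ρ) | Simulated SE ratio | Type I error, unpaired |
|---|---|---|---|---|
| 0.5 | 0.25 | 1.155 | 1.098 | 3.2% |
| 0.7 | 0.15 | 1.085 | 1.057 | 3.9% |
| 0.9 | 0.05 | 1.026 | 1.022 | 4.6% |

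The paired test stays at 4.9% to 5.1%.

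**4. Dependence on the mechanism.** Step 3 assumes that pairs are sorted on the same noisy baseline value that is later subtracted.

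- Pairs sorted on the underlying hospital level, with no true drift: SE ratio 0.995 to 1.003 and type I error 4.9% to 5.1% at every *r*.
- Pairs resting only partly on baseline outcome: type I error 4.2% to 5.1%, with the paired interval from 1% narrower to 2% wider than the unpaired one. The 2% is the price in degrees of freedom (57 = 59 − 2 against 28 = 29 − 1): 2.048/2.002 = 1.023.
- Pair mates sharing a drift for other reasons (realised correlation of change 0.24 and 0.42): type I error 2.2% and 1.0%. Power is then 99.1% unpaired against 99.6% paired, and 99.5% against 99.9%.

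**5. Power, net of degrees of freedom.** Power of the paired test, under the pairing of step 3, where the unpaired test has the plan's stated power:

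| r | Primary (97%) | Vancomycin (92%) | Antipseudomonal (84%) |
|---|---|---|---|
| 0.5 | 97.7% | 93.6% | 87.0% |
| 0.7 | 97.1% | 92.3% | 84.9% |
| 0.9 | 96.6% | 90.8% | 82.5% |
| 0.95 | 96.4% | 90.4% | 81.8% |

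Break-even lies near r = 0.75. The primary outcome moves by +0.7 to −0.6 points and the antipseudomonal outcome by +3.0 to −2.2. The plan's Monte Carlo intervals (91% to 99% and 77% to 91%) are much wider. If a pair term were dropped whenever its variance estimate was zero, type I error would be 5.2% to 5.6%.

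**6. The hospital index.** Suppose the three merged sets were entered as separate hospitals. With two hospitals per set, simulated type I error is 5.4% and 6.2% (within-set correlation of change 0.5 and 1). With three per set it is 6.6% and 8.1%. A separate simulation with four per set reaches 10.3%. Set sizes and correlations are assumptions, and the analysis itself would run against Protocol B.1.5.

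**The case for a change.** The best case for a change rests on the index rather than the pairs. Splitting merged hospitals is the only route here to an inflated primary test, and a programmer working from hospital identifiers could take it. The phrase about randomisation units appears only with the supportive models and could mean pairs or merged units. One sentence would settle it. On pairs, the argument is that only a paired analysis holds its nominal level whatever the correlation, and that the choice should be fixed before intervention-period results are seen.

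Part of this stands. The SAP's model text does not repeat the merging rule, and the phrase about randomisation units is not explained. A line on each would be harmless if the SAP were reopened for another reason. But the Protocol gives the rule in general terms and the power routine applies it, so nothing in the documents points to splitting.

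The pair choice is already fixed: the equation lists every term, and the primary analysis is declared unadjusted. The steadier coverage of a paired test is real where pairs are sorted closely on the analysed baseline or share a drift. It costs about half the degrees of freedom and needs a pair-by-period term, since a pair intercept alone would hardly touch the interaction. It also needs a rule for the unmatched unit. None of this has been tried in the Poisson mixed model.

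**Conclusion.** No change follows. Omitting pairs is a fair trade-off. For a non-negative correlation between pair mates' changes the primary test is neutral or conservative, never inflated. Its type I error is 3.2% to 4.6% for *r* of 0.5 to 0.9 if pairs are sorted exactly on the analysed baseline, and 4.2% to 5.1% if only partly. It falls lower only if pair mates share a substantial drift, and simulated power was then 99% or more either way. Under pairing on the analysed baseline, a paired analysis would move primary power by less than one point in either direction.

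The hospital index is a small gap in wording that the Protocol's randomisation section and the power routine fill: hospitals sharing stewardship staff are one unit. The inflation of 5.4% to 8.1% for sets of two or three describes an analysis that the documents do not plan.

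These figures rest on assumed values of *r*, set size and within-set correlation, and on unit-level t-tests rather than the planned mixed model. The direction of the pair result depends only on ρ not being negative.

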#### Table 1: INSPIRE-ASP UTI Extended-Spectrum Antibiotics

Pathogen-Directed Antibiotic Category	Extended-Spectrum Antibiotics Targeted in INSPIRE UTI CPOE Prompts
Anti-MRSA	Ceftaroline, Daptomycin, Linezolid  , Vancomycin 
Anti-VRE	Daptomycin, Linezolid
Anti-Pseudomonas	Aztreonam, Cefepime, Ceftazidime, Piperacillin/Tazobactam
Anti-ESBL	Ertapenem, Ceftolozane/Tazobactam, Meropenem, Imipenem
Anti-CRE	Ceftazidime/Avibactam, Colistin, Imipenem/Relebactam, Meropenem/Vaborbactam, Polymixin B, Tigecycline

Both oral and intravenous (IV) formulations, IV formulation only.

Abbreviations: **CPOE** – Computerized Physician Order Entry, **MRSA** - Methicillin Resistant *Staphylococcus aureus*, **ESBL** – Extended Spectrum Beta Lactamase Producing *Enterobacterales*, including multi-drug *Acinetobacter* and *Pseudomonas* species susceptible to Carbapenem. **VRE** – Vancomycin Resistant *Enterococci*, **CRE** – Carbapenem Resistant *Enterobacterales*.

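### Holm's step-down would give both secondary outcomes more power than a fixed 0.025 each, at the same 0.05 error for the pair

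*SAP*

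**What the plan says.** Three statements in the SAP section Primary Statistical Analysis, repeated in Protocol B.1.10, set the error rates for effectiveness.

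- Primary outcome: "The primary trial analysis will use an as-randomized unadjusted model with two-tailed significance set at alpha = 0.05".
- Trial success: "The assessment of trial success will be determined by the significance of the arm by period interaction term", which is the interaction term in the primary model.
- Secondary outcomes: the same kind of model, described as corrected for multiplicity. The level is given as "two-tailed significance set at alpha = 0.025 for the two secondary outcomes".

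Neither document names a step-down procedure, and neither makes the secondary tests conditional on the primary result. Neither claims that error is held at 0.05 across all three tests together.

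The safety tests are a separate set. For them the SAP states that "we do not intend to make adjustments for multiple comparisons in testing them". They play no part in this point.

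The power table (SAP Table 4, Protocol Table 5) gives 97% (91-99) for the primary, 92% (85-96) for vancomycin and 84% (77-91) for antipseudomonals. The alpha behind the two secondary figures is not stated.

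**The concern.** With two tests, a fixed 0.025 for each is the Bonferroni method, and Holm improves on it at the same family error. The plan therefore gives up some secondary power without gaining any error control. The outcome with most to gain is the antipseudomonal one, which already has the lowest stated power of the three.

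What is at stake is limited: the chance that a true effect on one secondary outcome goes undeclared because its p-value falls between 0.025 and 0.05 while the other outcome is clearly significant. The primary test and the declaration of trial success are not affected.

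**Working it through.** **Inputs from the documents.** Primary alpha is 0.05 two-tailed, and secondary alpha is 0.025 two-tailed for each of two outcomes. Stated power is 97% for the primary, 92% for vancomycin (V) and 84% for antipseudomonal (A).

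**Assumptions.** Test statistics are normal. The stated powers are taken as given, because they come from a bootstrap of hospital data that is not in the documents. Their alpha is unknown, so both 0.025 and 0.05 are carried. The correlation between the tests is not given. Independence is worked by formula, and other values come from simulation.

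**Step 1: the plan's own figure.** 0.05 / 2 = 0.025, as stated. The secondary family error is at most 2 × 0.025 = 0.05, or 1 − 0.975² = 0.0494 if the tests are independent.

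**Step 2: Holm keeps the same error.** If both null hypotheses are true, a false rejection needs at least one p-value at or below 0.025, and that probability is at most 0.025 + 0.025 = 0.05. If only one is true, a false rejection needs that p-value to be at or below 0.05, again at most 0.05. Neither bound depends on the correlation.

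**Step 3: power of each test at both levels.** The mean of the test statistic is z(alpha/2) + z(power), with z(0.0125) = 2.241 and z(0.025) = 1.960. Power at another level is Φ(mean − critical value).

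- Stated powers read at 0.025: V has mean 2.241 + 1.405 = 3.646, so power is 0.920 at 0.025 and 0.954 at 0.05. A has mean 2.241 + 0.994 = 3.236, so power is 0.840 and 0.899.
- Stated powers read at 0.05: V has mean 1.960 + 1.405 = 3.365, so power is 0.869 at 0.025 and 0.920 at 0.05. A has mean 1.960 + 0.994 = 2.954, so power is 0.762 and 0.840.

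**Step 4: power under Holm.** An outcome is rejected if its own p ≤ 0.025, or if its own p ≤ 0.05 and the other outcome's p ≤ 0.025. Under independence:

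Holm power = own power at 0.025 + (own power at 0.05 − own power at 0.025) × other's power at 0.025.

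- Read at 0.025, V: 0.920 + (0.954 − 0.920) × 0.840 = 0.949.
- Read at 0.025, A: 0.840 + (0.899 − 0.840) × 0.920 = 0.894.
- Read at 0.05, V: 0.869 + (0.920 − 0.869) × 0.762 = 0.908.
- Read at 0.05, A: 0.762 + (0.840 − 0.762) × 0.869 = 0.830.

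Simulation with correlated secondaries gives a smaller gain, but still a gain:

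| Alpha behind stated power | Outcome | Plan | Holm, independent | Holm, correlation 0.3 | Holm, correlation 0.7 |
|---|---|---|---|---|---|
| 0.025 | V | 0.920 | 0.949 | 0.944 | 0.936 |
| 0.025 | A | 0.840 | 0.894 | 0.891 | 0.888 |
| 0.05 | V | 0.869 | 0.908 | 0.902 | 0.890 |
| 0.05 | A | 0.762 | 0.830 | 0.826 | 0.822 |

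**Step 5: all three tests together, for context.** The ceiling under the global null is 0.05 + 0.025 + 0.025 = 0.10. Under independence it is 1 − 0.95 × 0.975² = 0.097. The primary sums over all extended-spectrum drugs, including intravenous vancomycin and the antipseudomonals "Aztreonam, Cefepime, Ceftazidime, Piperacillin/Tazobactam", so positive correlation is expected. In simulation the rate is about 0.088 with correlation 0.5 to the primary and 0.3 between secondaries, and about 0.062 with 0.9 and 0.7.

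**Step 6: adding a gate on the primary.** If the secondaries were tested only after a significant primary, overall error would be 0.05. Under independence, secondary power is Holm power times primary power. With the stated powers read at 0.025:

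- Primary power 97%: V 0.949 × 0.97 = 0.920, against 0.920 in the plan. A 0.894 × 0.97 = 0.867, against 0.840.
- Primary power 91%, the lower limit in the documents: V 0.863 and A 0.814, both below plan. At the highest correlations tried they are 0.900 and 0.872.
- Break-even primary power: V 0.920 / 0.949 = 0.970; A 0.840 / 0.894 = 0.939. With the stated powers read at 0.05 these become 0.958 and 0.918.

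**The case against.** The strongest objection is that nothing here is broken. Trial success rests on a single test at 0.05, and the secondary pair is separately held at 0.05. Separate control of the two families is a recognised design choice. That stands, and it limits the point to a refinement.

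A reader might go further and infer that the plan has nearly double its nominal error because the three alphas sum to 0.10. The documents do not support that. They never set 0.05 as a target across all three tests, 0.10 is only a ceiling, and the shared drugs make the true rate probably lower.

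A reader might also infer that gating on the primary plus Holm is a free improvement. It is not, because the gate removes secondary power whenever the primary fails. At the planned 97% primary power vancomycin only breaks even under independence, and at 91% it loses. There is also a substantive case against a gate: the prompts are specific to pathogen and drug category (Protocol B.1.2), so an effect confined to one category is plausible even when the summed outcome misses significance.

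Two further objections carry some weight. A fixed 0.025 pairs directly with 97.5% confidence intervals, whereas Holm has no simple matching intervals. The gain, about 3 to 7 percentage points under independence, is also no larger than the uncertainty in the stated powers. Neither overturns the point, because Holm is never worse than the fixed level for either outcome, whatever the true powers are.

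**Conclusion.** The point holds as a minor improvement, not as an error. At the same 0.05 error for the secondary pair, Holm raises power under independence by 2.9 points for vancomycin and 5.4 for antipseudomonals if the stated powers are at 0.025. If they are at 0.05, the gains are 3.9 and 6.8 points. Positive correlation between the two secondary tests shrinks these gains: at 0.7 they are 1.6 and 4.8 points, or 2.1 and 6.0.

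The error bound and the statement that Holm never loses power need no assumption about correlation. The sizes rest on normal test statistics and on the documents' power figures, which cannot be recomputed from what is given.

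**What to change.** In the SAP section Primary Statistical Analysis and in Protocol B.1.10, replace the fixed level with: the two secondary outcomes will be tested by Holm's procedure at a family two-sided level of 0.05, the smaller p-value at 0.025 and, if significant, the other at 0.05. Make the change before outcomes are compared by arm.

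State also that 97.5% confidence intervals will be reported for both outcomes. Note that, where the larger p-value lies between 0.025 and 0.05, its interval may include no effect although Holm declares significance. State the alpha used for the secondary powers in SAP Table 4 and Protocol Table 5.

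The cost is one or two sentences in each document, with no change to sample size, data or conduct.

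Optional: if the sponsor wants 0.05 control across all three tests, add the condition that the secondaries are tested only after a significant primary. This should be a deliberate choice, since it costs secondary power if primary power falls below plan. If the sponsor keeps the secondaries ungated, one sentence should say what may be claimed from them when the primary fails.
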